## **6.6 Source Documents**

Source data is all information, original records of clinical findings, observations, or other activities in a clinical trial necessary for the reconstruction and evaluation of the trial. Source data are contained in source documents. Examples of these original documents, and data records include: hospital records, clinical and office charts, laboratory notes, memoranda, subjects' diaries or evaluation checklists, pharmacy dispensing records, recorded data from automated instruments, copies or transcriptions certified after verification as being accurate and complete, microfiches, photographic negatives, microfilm or magnetic media, x-rays, subject files, and records kept at the pharmacy, at the laboratories, and at medico-technical departments involved in the clinical trial.

## **6.7 Case Report Forms**

The study case report form (CRF) is the primary data collection instrument for the study. All data requested on the CRF must be recorded in a digital RedCap database system. All missing data must be explained. If a space on the CRF is left blank because the procedure was not done or the question was not asked, write "N/D". If the item is not applicable to the individual case, write "N/A". All entries should be printed legibly in black ink. If any entry error has been made, to correct such an error, draw a single straight line through the incorrect entry and enter the correct data above it. All such changes must be initialed and dated. DO NOT ERASE OR WHITE OUT ERRORS. For clarification of illegible or uncertain entries, print the clarification above the item, then initial and date it.

CONFIDENTIAL

This document and information is the property of the NYU School of Medicine and Langone Medical Center. Do not disclose or use except as authorized in writing by the study IND sponsor

## **6.8 Data Management**

### **Data Management**

The data for this study will be entered into the REDCap, a research data management system. The reports, record locking at case report form (CRF) and subject level and the paperless query features allow for the cleaning of data throughout the clinical study. The system has extensive security features and all data transmitted into or out of the REDCap database will be encrypted.

Study Data Management staff will conduct data management and data quality assurance work activities for the A Pilot Study to Evaluate the Effects of Everolimus on Brain mTOR activity and Cortical Hyperexcitability in Tuberous Sclerosis Complex (TSC) and Focal Cortical Dysplasia (FCD) study. Data Management staff will be responsible for the integrity of all study data. They will review and monitor the completeness and accuracy of data thought out the duration of the study. Final data clean up will be completed shortly after the last subject visit and the study database will be locked and provided to the study statistician for analyses.

A CRF will be completed for each subject. This CRF has proven successful in previous studies. It is the investigator's responsibility to ensure the accuracy, completeness, clarity, and timelines of the data reported in the subject's CRF. Source documentation supporting the CRF data should indicate the subject's participation in the study and should document the dates and details of study procedures, adverse events, other observations, and subject status.

The investigator, or designated representative, should complete the CRF as soon as possible after information is collected. An explanation should be provided for all missing data.

The PI, [name], will provide the study site with CRF training sufficient to permit site personnel to enter or correct information in the CRFs for the subjects for which they are responsible.

### **6.8.1 Data Collection Forms: To be submitted by study coordinator**

Within 48 hours of registration completion: On-study CRF, Signed, Dated Consent, On-Study Lab Reports, Medical History CRF, Eligibility Checklist; Within two weeks of registration: Pre-Operative Evaluation CRF, Completed Subject Diaries, Complete Lab test results; Within two weeks post surgery: Post-Op evaluation CRF, Off-Study Evaluation CRF; Within two weeks post-surgery, within 30 days for all other AE's: Toxicity CRFs; Within 24 hours of event occurrence: SAE's Hospitalization Admission/Discharge Summaries

### **6.8.2 Subject Identifiers**

Each patient will be given a unique identifier (study number) in the order of enrollment. Each blood and tissue sample will be placed in an individual cryotube labeled with study number, date of surgery, and time of collection.

### **6.8.3 Confidentiality**

Each subject enrolled will, from that point forward, be identified by a unique identifier (study number). This study number will also be used for research specimens collected and shipped to collaborating laboratories. Clinical information will be accessed, according to HIPAA requirements, by study personnel to complete study documents, as needed. Only the PI and the study coordinator will have access to the log linking the study number to the patient name, birth date, and medical record number. The log will be kept in a secure file.

CONFIDENTIAL

This document and information is the property of the NYU School of Medicine and Langone Medical Center. Do not disclose or use except as authorized in writing by the study IND sponsor

Medical and study records will be kept in accordance with state and federal laws concerning the privacy and confidentiality of medical information. The confidentiality of each subject's medical record is also protected by federal privacy regulations.

Subjects will be informed of all protected health information used in this study. The consent form will seek written permission from the patient to use and disclose information for this research. The patient or parent is required to sign this form. This Authorization will not expire unless the patient withdraws it in writing. The volunteer has the right to withdraw authorization at any time, except to the extent that NYU has already relied upon it or must continue to use the information to complete data analysis or to report data for this study.

#### **6.8.4 Disposition of Data**

Research findings will be stored in a password protected computer. Written and electronic records, reports, and data resulting from this clinical trial will be kept in the volunteer's research record for at least six years or until the study is completed, whichever is longer. At that time, either the research information not already in the medical record will be destroyed or information identifying the patient will be removed from such study results at NYU. Any research information in the medical record will be kept indefinitely.

#### **6.8.5 Sharing Study Results**

We plan to make all data and resources generated under this grant available to the academic community immediately after we report them for the first time in a peer-reviewed publication. Results used in publications will not be identifiable or able to be traced back to enrolled subjects.

### **6.9 Records Retention**

It is the investigator's responsibility to retain study essential documents for at least 6 years after the study is completed and the database is locked for analysis.

## **7 Study Monitoring, Auditing, and Inspecting**

### **7.1 Study Monitoring Plan**

The Principal Investigator ([name]) will follow the data safety monitoring plan below to ensure that all safety measures are taking place in the best interest of the subjects.

#### **Data Safety Monitoring Plan (DSMP)**

*Who will do the data monitoring for this study:*

- The PI, [name].
- The sub investigator, [name]
- The independent monitor, [name]

*Explain how data safety will be monitored:*

- Drug tolerability and safety will be monitored during clinical evaluations and phone visits by investigator/study team member that will seek information on adverse events by specific questioning and, as appropriate, by examination.
  - .
- [name], [name] and [name] will review all patients during the treatment period and throughout the post-treatment period. They will review all cases and if it is deemed that the serious adverse event(s) are related to study drug, the study will be terminated for that subject. If two patients among the 9 treated with everolimus develop a) impaired surgical wound healing or if three patients among the 9 develop b) serious infection, including wound site infection, study termination will occur. Any case of wound site infection complicated by a wound healing problem will NOT be considered a wound healing problem, but secondary to the infection.

**CONFIDENTIAL**

This document and information is the property of the NYU School of Medicine and Langone Medical Center. Do not disclose or use except as authorized in writing by the study IND sponsor

- There is a risk of PHI dissemination. All personal health information (on paper) will be stored at NYU Comprehensive Epilepsy Center located at [name] in a locked filing cabinet. Patient information may also be stored in REDCap, a secure research data management system. Only personnel listed on the study will have access to PHI.

*Describe any potential conflict of interest the DSM contact may have:*

None.

#### **Data Safety Monitor Details:**

*The enrolled subjects will be monitored:*

Drug

- Patients will be routinely monitored for adverse events via clinical evaluations and phone visits
- Subjects will have the research coordinator's phone number to call in case of need to report side effects on days not scheduled for clinical evaluation or phone visit.

PHI

- All PHI will be kept in locked filing cabinet at NYU Comprehensive Epilepsy Center and/or entered into REDCap (NYU secure data management system) with access given only to study personnel

*Dropouts will be monitored:*

- Dropouts will have a final visit to complete their enrollment and receive instructions for tapering off of Everolimus.

.

*Primary and secondary efficacy endpoints will be monitored:*

The primary study endpoints of the safety and tolerability of everolimus in children and young adults and the establishment of optimal dose will be monitored via:

- Side Effects in children and subjects where caregiver reports and in adults that are able to self report.
- Evaluation of seizure diary at clinical evaluations and phone visits

The secondary study endpoint of change in frequency from baseline will be monitored via:

- Evaluation of seizure diary at clinical evaluations and phone visits

*Reportable events will be monitored using an accepted scale:*

No, there will be no accepted scale for monitoring reportable events. All reportable events will be followed until resolution, stabilization, or until it has been determined that the study treatment or participation is not the cause. If the reportable event is still ongoing at the end of the study, it will be followed until final outcome has been reached.

*Describe the frequency of monitoring:*

The Independent monitor will evaluate every 12 months after the first patient receives the initial dosage of everolimus

*Interim analysis will take place:*

No, interim analysis will not take place unless requested by the IRB.

#### **Reportable events**

*This protocol will adhere to NYU SOM IRB policy for reportable events reporting:* Yes, we will adhere to the policy for reportable events. We will also be reporting to Novartis Pharmaceuticals Corporation.

#### **Description of Data Safety Monitoring**

##### **1. Types of data and events that will be captured under the DSMP**

The only type of event that we anticipate to capture is from subjects who have adverse side effects from drug or whose PHI was accidentally disseminated.

CONFIDENTIAL

This document and information is the property of the NYU School of Medicine and Langone Medical Center. Do not disclose or use except as authorized in writing by the study IND sponsor

**2. Responsibilities and roles for gathering, evaluating and monitoring data**

[name], Dr.[name], and [name] (the independent monitor) will be responsible for evaluating and monitoring data. They will oversee the DSMP andDSMR.

**3. Information about the monitoring entity**

The independent monitor, [name], is the monitoring entity.

**4. Reportable events that will be reported to the monitoring entity and when the events will be reported**

Yes, all reportable events will be immediately reported to the PI by the independent monitor, study personnel, co-investigators or anyone who is aware of a reportable event. Reportable events may be reported by email or by phone to the PI.

**5. Assessment for the frequency of monitoring**

We will submit a Data Safety Monitoring Report every 12 months, at the same time as the annual renewal. If there is a reportable event, the independent monitor or other study personnel will report it to the IRB immediately.

**6. Stopping rules and criteria for withdrawal of subjects**

Subjects may withdraw from the study at the request of the parent or legal guardian for side effects that impair function or quality-of-life, assuming they do not want to lower the dose to a tolerable range. Subjects will also have drug discontinued by investigator if any serious adverse effect is identified and considered as a possible or definite result of the study medication. These include rash, other signs of hypersensitivity, or liver function tests that exceed baseline or normal measures by 50%. Clinical judgment will be used when determining need for everolimus therapy to be terminated. Other reasons for withdrawal include non-compliance with study procedures, seizure exacerbation, or interaction with current concomitant AED therapy. The method termination of everolimus therapy will be determined based on type of reaction and/or reason for withdrawal.

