## **4 Subject Selection and Withdrawal**

### **4.1 Inclusion Criteria (Active Group)**

1. Female and male patients, age 2 years to 50 years.
2. Diagnosis: treatment resistant epilepsy ( $\geq 2$  failed anti-epileptic drug [AED] treatment regimens) and either:
  - Tuberous Sclerosis Complex
  - Focal Cortical Dysplasia on MRI or neuropathology from prior brain surgery
3. Diagnosis of TSC confirmed by genetic testing and/or clinically definite diagnosis of TSC according to the modified Gomez criteria [31]. Clinically definite diagnosis is defined as:
  - Two Major Features, or
  - One Major Feature plus two Minor Features
4. Adequate bone marrow function as shown by: ANC  $\geq 1.5 \times 10^9/L$ , Platelets  $\geq 100 \times 10^9/L$ , Hb  $> 9$  g/dL;
5. Adequate liver function as shown by
  - a. Total serum bilirubin  $\leq 2.0$  mg/dL,
  - b. ALT and AST  $\leq 2.5 \times$  ULN ( $\leq 5 \times$  ULN in patients with liver metastases),
  - c. INR  $\leq 2$ ; if applicable
6. Adequate renal function: serum creatinine  $\leq 1.5 \times$  ULN;
7. Fasting serum cholesterol  $\leq 300$  mg/dL OR  $\leq 7.75$  mmol/L AND fasting triglycerides  $\leq 2.5 \times$  ULN. if applicable NOTE: In case one or both of these thresholds are exceeded, the patient can only be included after initiation of appropriate lipid lowering medication;
8. Signed informed consent obtained prior to any screening procedures.

CONFIDENTIAL

This document and information is the property of the NYU School of Medicine and Langone Medical Center. Do not disclose or use except as authorized in writing by the study IND sponsor

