**Table 3: Dosing guidelines for Everolimus-related non-hematologic toxicities**

CONFIDENTIAL

This document and information is the property of the NYU School of Medicine and Langone Medical Center. Do not disclose or use except as authorized in writing by the study IND sponsor

Toxicity	Action
AST or ALT elevation	Maintain current dose level
Grade 1 (> ULN - 3.0 x ULN)	
Grade 2 (> 3.0 - 5.0 x ULN)	
AST or ALT elevation	Interrupt Everolimus administration until resolution to $\leq$ grade 1 (or $\leq$ grade 2 if baseline values were within the range of grade 2). If resolution occurs $\leq$ 7 days, Everolimus should be re-started at the dose level prior to interruption.
Grade 3 (> 5.0 - 20.0 ULN)*	If resolution takes $>$ 7 days, or if event recurs within 21 days, hold Everolimus until recovery to $\leq$ grade 1 or baseline grade/ value and reintroduce Everolimus at one dose level lower, if available.
AST or ALT elevation	Interrupt Everolimus administration until resolution to $\leq$ grade 1 (or $\leq$ grade 2 if baseline values were within the range of grade 2). If resolution occurs $\leq$ 7 days, Everolimus should be re-started at one dose level lower. If resolution takes $>$ 7 days, discontinue Everolimus.
Grade 4 (> 20 x ULN)*	
Recurrence of grade 4 after dose reduction or toxicity requiring Everolimus interruption for $>$ 21 days	Discontinue Everolimus.
Intolerable grade 2 mucositis, or grade 3 AE, except hyperglycemia or hypertriglyceridemia or hypercholesterolemia	Interrupt Everolimus administration until resolution to $\leq$ grade 1 or baseline grade / value. If resolution occurs within $\leq$ 7 days, Everolimus should be re-started at the dose level prior to interruption. If resolution takes $>$ 7 days, or if event recurs within 21 days, hold Everolimus until recovery to $\leq$ grade 1 or baseline grade/ value and reintroduce Everolimus at one dose level lower, if available. Patients will be withdrawn from the study if they fail to recover to $\square$ grade 1 or baseline grade / value within 21 days.
Any other grade 4	Hold Everolimus until recovery to grade $\square$ 1 or baseline value Reintroduce Everolimus at one dose level lower, if available.
Grade 3 or 4 clinical liver failure (asterixis or encephalopathy/coma)	Discontinue Everolimus

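### Section 7.1 discontinues everolimus for drug-attributed liver tests 50% above baseline or normal, while Table 3 keeps the dose unchanged for everolimus-related AST/ALT elevations up to 5.0 x ULN

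*Combined protocol and SAP*

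**What the plan says.** **Section 7.1, Description of Data Safety Monitoring, item 6.** "Subjects will also have drug discontinued by investigator if any serious adverse effect is identified" and is "considered as a possible or definite result of the study medication". The effects named as included are rash, other signs of hypersensitivity, and "liver function tests that exceed baseline or normal measures by 50" percent. The item then adds: "Clinical judgment will be used when determining need for everolimus therapy to be terminated".

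**Section 5.3.1, Table 3 (everolimus-related non-hematologic toxicities).** AST or ALT elevation of "Grade 1 (> ULN - 3.0 x ULN") and "Grade 2 (> 3.0 - 5.0 x ULN") share one action: "Maintain current dose level". For Grade 3, everolimus is interrupted and restarted at the previous dose if the elevation resolves within 7 days. For Grade 4, it is interrupted and restarted one dose level lower if it resolves within 7 days.

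**Section 4.1, inclusion item 5.** Under "Adequate liver function as shown by", part b admits ALT and AST up to 2.5 x ULN, or up to 5 x ULN in patients with liver metastases.

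**Section 5.3.** Treatment ends if a Grade 3 or 4 adverse event occurs, and an interruption for toxicity leads to discontinuation.

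**Section 4.4.1.** A subject who develops a Grade 3 or 4 event is withdrawn.

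**Scheduled blood work.** Visit 2 and the infection surveillance under Medical Monitoring (section 6.5) list a blood count and C-reactive protein. Visit 2a adds an everolimus level for three-week patients. The day-of-surgery sample is for everolimus level, cytokines and mTOR activity.

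**The concern.** An investigator who sees a raised, drug-attributed ALT in a treated patient finds one section that stops the drug and another that leaves the dose alone. Nothing says which section governs, or whether the 50% is measured from the patient's own baseline or from normal. Two investigators could act in opposite ways on the same value and both point to the protocol.

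The first stake is patient safety, in a study that describes its safety analyses as primary. The second is the S6 comparison. Everolimus is otherwise taken through the morning of surgery, the stated half-life is 30 hours, and every patient who undergoes surgery enters the S6 analysis, with no stated exclusion for early discontinuation. The rule applied could therefore decide whether a treated patient's tissue is obtained on or off drug.

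**Working it through.** The plan gives no figure to reproduce here. The check puts each threshold on the x ULN scale. It is confined to AST and ALT, because those are the tests in the Table 3 rows.

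**Inputs**
- Section 7.1 item 6: more than 50% above the reference, so threshold = 1.5 x reference. The reference is either normal (taken as ULN, an assumption) or the patient's baseline.
- Table 3: dose maintained from above 1.0 to 5.0 x ULN (Grades 1 and 2).
- Entry cap, section 4.1 item 5b: 2.5 x ULN without liver metastases.

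**Reading A: reference is normal (ULN).** Threshold = 1.5 x 1.0 = 1.5 x ULN. Values from above 1.5 to 5.0 x ULN mean discontinue under section 7.1 and maintain under Table 3. The top of Grade 2 is (5.0 − 1.0) / 1.0 = 400% above ULN, against a stopping threshold of 50%.

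**Reading B: reference is the patient's baseline.** Threshold = 1.5 x baseline.

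| Baseline (x ULN) | Item 6 threshold (x ULN) | Range of opposite actions (x ULN) |
|---|---|---|
| 0.5 | 0.75 | above 1.0 to 5.0 |
| 1.0 | 1.5 | above 1.5 to 5.0 |
| 2.0 | 3.0 | above 3.0 to 5.0 |
| 2.5 (entry cap) | 3.75 | above 3.75 to 5.0 |

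The range disappears only when 1.5 x baseline reaches 5.0, that is, at a baseline of 5.0 / 1.5 = 3.33 x ULN. That is above the 2.5 cap and can be reached only under the liver-metastases exception. Every patient admitted under the 2.5 cap therefore has a range of conflict on either reading.

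**Before the first dose.** On reading A, a patient who enters at above 1.5 to 2.5 x ULN (50% to 150% above ULN) already exceeds the number. On reading B nobody does, since a value cannot exceed itself by 50%. On neither reading is the whole criterion met, because item 6 also requires the effect to be a possible or definite result of the drug.

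**Grades 3 and 4.** Table 3 interrupts and then restarts. Section 5.3 turns an interruption for toxicity into discontinuation, and section 4.4.1 withdraws the subject. These cannot all be followed for the same event.

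**What would trigger either rule.** None of the scheduled on-treatment blood work listed in the visit and surveillance sections is identified as a liver test.

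**The case against.** The strongest defence is that neither text is a rigid rule. Item 6 ends with clinical judgment, it speaks of serious effects attributed to the drug, and section 5.3.1 presents its tables as recommendations and guidelines. A sensible investigator would not stop treatment mechanically at 1.5 x ULN. This softens the conflict but does not remove it. Discretion over whether to stop does not say which threshold applies. The attribution condition does not separate the rules, because Table 3 is itself confined to everolimus-related toxicity. The word serious does not help either, because item 6 names the 50% elevation as one of the included effects.

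Three stronger readings are tempting, and the documents do not support them.

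- *An eligible patient could meet the stopping criterion before the first dose.* Only the number can be exceeded then, and only if normal means ULN. The attribution condition cannot be satisfied before dosing.
- *Three liver thresholds conflict with one another.* The 2.5 x ULN entry limit is compatible with Table 3. For Grades 1 and 2, the contradiction is between item 6 and Table 3.
- *The primary results are shown to be affected.* One treated patient is 1/9 = 11% of the arm, but that is the weight of one patient and not an estimated effect. No expected frequency is given, no discontinuation count is named as a primary result, and the quantified safety rule concerns wound healing and serious infection. With no on-treatment liver test visible in the schedule, neither rule would be triggered routinely.

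**Conclusion.** The contradiction is real and unresolved. For drug-attributed AST/ALT elevations, section 7.1 item 6 and Table 3 direct opposite actions from above 1.5 to 5.0 x ULN if normal means ULN. On the baseline reading, the range runs from above 1.5 x baseline (or from above ULN, where 1.5 x baseline falls below it) to 5.0 x ULN. The lower edge rests on the undefined reference; the upper edge is Table 3's own.

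A further weakness holds on the normal reading. For a patient admitted at above 1.5 to 2.5 x ULN, the number cannot separate a pre-existing elevation from a drug effect. The Grade 3 and 4 entries in Table 3 are separately inconsistent with sections 5.3 and 4.4.1.

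The consequences for exposure at surgery and for the S6 comparison are possible, but the documents do not allow them to be quantified. This is an internal inconsistency that should be corrected because it bears on safety and is cheap to fix; it is not a demonstrated bias.

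**What to change.** Reconcile section 7.1 item 6, Table 3, section 5.3 and section 4.4.1, and check the result against inclusion item 5b. One liver-test rule should then apply throughout. It should state the reference value (baseline, ULN, or both with an order), the handling of a patient who enters with an elevated value, and which section takes precedence. The sponsor's medical lead decides the content of the rule; this review takes no position on it.

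In the same edit, confirm whether a liver test is scheduled during treatment, and list it in the visit schedule if it is. If values are expected only from routine pre-surgical care, say so.

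The cost is a wording amendment across about four sections, with no change to sample size or analysis. If it turns out that an on-treatment liver test has to be added, that is an additional procedure, with its own cost.
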